2.1.2 General analysis conventions

Pooling of centers: Unless specified otherwise, data from all study centers will be pooled for the analysis. Due to expected small number of patients enrolled at centers, no center effect will be assessed.

Qualitative data (e.g., gender, race, etc.) will be summarized by means of contingency tables; a missing category will be included as applicable. Percentages will be calculated using the number of patients in the relevant population or subgroup as the denominator.

Quantitative data (e.g., age, body weight, etc.) will be summarized by appropriate descriptive statistics (i.e. mean, standard deviation, median, minimum, and maximum). PK parameters except Tmax will be summarized by appropriate descriptive statistics (n, arithmetic

mean, CV% mean, standard deviation (SD), median, geometric mean, CV% geo-mean, minimum and maximum).

2.1.3 General definitions

Study drug and Study treatment

The study drug/study treatments for this study is eltrombopag (ETB115).

Eltrombopag will be supplied as film-coated tablets (25 mg) provided either as commercial packages locally.

Date of first administration of study treatment

The date of first administration of study treatment will be derived as the first date when a nonzero dose of study treatment is administered and recorded on the appropriate CRF.

Date of last administration of study treatment

The date of last administration of study treatment will be derived as the last date when a nonzero dose of study treatment is administered and recorded on the appropriate CRF. For those patients still on treatment at cutoff date, the cutoff date will be imputed as the date of last administration of study treatment.

Study day

The study day, describes the day of the event or assessment date, relative to the reference start date.

The study day is defined as:

- The date of the event (visit date, onset date of an event, assessment date etc.) – reference start date + 1 if event is on or after the reference start date;
- The date of the event (visit date, onset date of an event, assessment date etc.) – reference start date if event precedes the reference start date.

The reference date for all assessments (safety, efficacy, pk, etc) is the date of first administration of study treatment as defined above. The study day will be displayed in the data listings.

Time unit

A year length is defined as 365.25 days. A month length is 30.4375 days (365.25/12). If duration is reported in months, duration in days will be divided by 30.4375. If duration is reported in years, duration in days will be divided by 365.25.

Baseline

For safety and efficacy evaluations, the last available assessment on or before the date of first administration of study treatment is defined as “baseline” assessment. If patients have no value as defined above, the baseline result will be missing.

On-treatment assessment/event and observation periods

The overall observation period will be divided into three mutually exclusive segments:

1. ***pre-treatment period***: from day of patient's informed consent to the day before first administration of study treatment
2. ***on-treatment period***: from date of first administration of study treatment to 30 days after date of last actual administration of study treatment (including start and stop date)
3. ***post-treatment period***: starting at day 30+1 after last administration of study treatment.

Safety summaries (tables, figures) include only data from the on-treatment period with the exception of baseline data which will also be summarized where appropriate (e.g. change from baseline summaries). In addition, a separate summary for death including on treatment and post treatment deaths will be provided. In particular, summary tables for adverse events (AEs) will summarize only on-treatment events, with a start date during the on-treatment period (***treatment-emergent*** AEs).

However, all safety data (including those from the post-treatment period) will be listed and those collected during the pre-treatment and post-treatment period will be flagged.

Windows for multiple assessments

In order to summarize hematological response collected over time (including unscheduled visits), the assessments will be time slotted. The following general rule will be applied in creating the assessment windows: If more than one assessment is done within the same time window, the assessment performed closest to the target date will be used. If 2 assessments within a time window are equidistant from the target date, then the earlier of the 2 assessments will be used. Data from all assessments (scheduled and unscheduled), including multiple assessments, will be listed.

Table 2-1 Time windows for hematological response

Assessment	Target day of assessment	Time Interval
Baseline	On or before Study Day 1	≤ Day 1
Week 13	Week 13 ± 3 days	Study Day 77 – 105 (i.e. 11 to 15 weeks)
Week 26	Week 26 ± 3 days	Study Day 168 – 196 (i.e. 24 to 28 weeks)
Week 52	Week 52 ± 3 days	Study Day 336 – 392 (i.e. 48 to 56 weeks)

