2.5.1 Primary endpoint

The primary endpoint is the hematologic response rate at Week 26, which is defined as the proportion of all subjects who meet any of the International Working Group (IWG) criteria at Week 26 shown in the table below. The primary endpoint will be based on the investigator assessment of response.

The analysis for primary endpoint as well as related supplementary and supportive analysis will not be reproduced for final CSR.

The primary analysis will be based on FAS and will include all data observed up-to the cut-off date.

Table 2-2 IWG criteria for Primary Endpoint

Assessment Item	Baseline transfusion status	Response Criteria
Platelet count	Platelet transfusion independent	Transfusion independent ⁽¹⁾ and increase from baseline by $20 \times 10^9/L$ or more
	Platelet transfusion dependent	No platelet transfusion requirement for 8 weeks
Hemoglobin	RBC transfusion independent	When the baseline hemoglobin level is < 90 g/L: transfusion independent and increase from baseline by 15 g/L or more
	RBC transfusion dependent	A decrease of at least 4 units in RBC transfusions in the post-treatment 8-week period (1 unit = RBC derived from 200 mL blood) Or no RBC transfusion requirement for 8 weeks (less than 4 units RBC in 8-week period at Baseline)

Assessment Item	Baseline transfusion status	Response Criteria
Neutrophil count	NA	(In the absence of G-CSF taken within 21 days preceding the blood sample collection) Increase from baseline by $0.5 \times 10^9/L$ or more, or (if $< 0.5 \times 10^9/L$ at baseline) increase by 100% or more

Note: No platelet/RBC transfusion requirement for 8 weeks means there is no any platelet/RBC transfusion received by patients during (Visit date-56 days) until Visit date. This definition also applies to Week 13 and Week 52.

(1) Transfusion independent means subjects did not receive platelet transfusion in the 4 weeks before Visit date.

During regular hematologic assessment, the exclusion period of transfusion and G-CSF are detailed below:

Platelet transfusion: 7 days preceding the assessment of platelet count

RBC transfusion: 14 days preceding the assessment of hemoglobin

G-CSF: 21 days preceding the assessment of neutrophil count

Definition of baseline Platelet Transfusion Independence/Dependence and platelet count

Baseline platelet transfusion independence/dependence and platelet count are defined as:

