- For platelet transfusion independent subjects that did not receive platelet transfusions in the 4 weeks before Day 1(include Day 1): The average of the most recent 2 platelet counts before Day 1(include Day 1).
- For transfusion dependent subjects that received one or more platelet transfusions in the 4 weeks before Day 1(include Day 1): The average of the most recent 2 platelet counts before Day 1 (excluding platelet counts within 6 days * following a platelet transfusion). If all platelet counts available are within 6 days* following a platelet transfusion, the lowest platelet count prior to initiation of study drug will be used as the baseline platelet count.

*: e.g. When a platelet transfusion was done on December 2nd (Monday), the platelet count will become usable from December 9th (Monday).

Definition of baseline RBC Transfusion Independence/Dependence and hemoglobin value

Baseline RBC transfusion independence/dependence and hemoglobin value are defined as:

- For RBC transfusion independent subjects that did not receive RBC transfusions in the 8 weeks before Day 1(include Day 1): The most recent hemoglobin value before Day 1(include Day 1).
- For RBC transfusion dependent subjects that received one or more RBC transfusions in the 8 weeks before Day 1(include Day 1): The last hemoglobin value prior to the most recent RBC transfusion. If no values exist prior to a RBC transfusion, the lowest value before Day 1(include Day 1) will be used.

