2.7.1 Secondary endpoints

The following analyses Changes in platelet count, hemoglobin and neutrophil count, Duration of hematological response, Maximum duration of Platelet and RBC transfusion independence will be generated for the final CSR.

Hematological Response at Week 13 and Week 52

Hematologic response rate at Week 13 and Week 52 will also be assessed by investigator according to the International Working Group (IWG) criteria for the primary endpoints shown in the [Table 2-2](#) above.

The analysis for hematologic response rate at Week 13 will only be produced at primary analysis, and hematologic response rate at week 52 will only be produced at updated analysis.

Changes in platelet count, hemoglobin and neutrophil count

Value and changes in platelet count (in the absence of platelet transfusion), hemoglobin (in the absence of RBC transfusion) and neutrophil count (in the absence of G-CSF) will be calculated according to the lab test results entered into CRF.

Time to hematological response

Time to hematological response is defined as the time from the date of first study drug administration to the first hematological response which is defined in [Section 2.5.1](#). All subjects in the FAS will be included in the time to hematological response calculations.

These will be analyzed and plotted for four assessment criteria: Hematological Response; Platelet/Platelet Transfusion; Hemoglobin/RBC Transfusion; Neutrophils.

The analysis for time to hematological response will only be produced at primary analysis.

Duration of hematological response

For subjects who responded, duration of hematological response will be defined as the number of months from the first date of a hematological response which is defined in [Section 2.5.1](#) until the first date of a relapse (defined as not meeting the response criteria) or a death. Only subjects with at least 2 response assessments are included in the duration of response assessment. Patient still responding at the cut-off date will be censored at date of last response assessment.

These will be analyzed and plotted for four assessment criteria: Hematological Response; Platelet/Platelet Transfusion; Hemoglobin/RBC Transfusion; Neutrophils.

Frequency and amount of transfusion

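### SAP 2.1.3 and 2.5.1 give different efficacy baselines for platelets and hemoglobin, and the count-change endpoint names neither, so a transfused baseline may be set against transfusion-restricted later values

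*SAP*

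**What the plan says.** SAP 2.1.3 defines baseline once for all purposes: "For safety and efficacy evaluations, the last available assessment on or before the date of first administration of study treatment". Efficacy is named, recent transfusion is not excluded, and no exception is made for definitions given elsewhere.

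SAP 2.5.1, which follows protocol 8.3.1, sets other rules for two of the three lineages:

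- **Platelets.** A mean of two counts is used. For transfusion-dependent subjects it is "The average of the most recent 2 platelet counts before Day 1 (excluding platelet counts within 6 days * following a platelet transfusion"). If every available count falls in that period, "the lowest platelet count prior to initiation of study drug will be used as the baseline platelet count".
- **Hemoglobin.** For RBC-dependent subjects: "The last hemoglobin value prior to the most recent RBC transfusion", or the lowest pre-treatment value if there is none. For RBC-independent subjects, the latest value.
- **Neutrophils.** No special baseline.

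SAP 2.7.1 defines the count-change endpoint as "Value and changes in platelet count (in the absence of platelet transfusion), hemoglobin (in the absence of RBC transfusion"), with a matching G-CSF restriction for neutrophils, and says that it "will be calculated according to the lab test results entered into CRF". No baseline is named there, in SAP 2.7.2 or in protocol 12.5.1. By contrast, SAP 2.7.1 ties Week 13 and Week 52 response to Table 2-2, and time to response and duration to Section 2.5.1. The count-change analysis is one of those generated again for the final CSR.

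**The concern.** The endpoint is meant to show change free of transfusion effects. Protocol 12.5.2 already provides a separate laboratory summary that ignores transfusion and G-CSF, so the restricted version exists for that reason. If the restriction acts on later values but not on the baseline, the transfusion effect comes back on one side of the subtraction. The likely direction is against the drug, and it would appear in the subjects who were being transfused at entry. Two programmers following the SAP could also produce different tables, and both could defend them.

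**Working it through.** **1. The plan's own figures.** The documents give no figure for this point. The response-rate table (protocol 12.8.1, SAP 3.1) does not depend on the count-change baseline. Its exact 90% limits for 8 of 20 are the 0.05 quantile of Beta(8, 13) and the 0.95 quantile of Beta(9, 12), which give 21.7% and 60.6% as stated.

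**2. The two rules side by side.**

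| Subject | Baseline under SAP 2.1.3 | Baseline under SAP 2.5.1 |
|---|---|---|
| RBC-independent, hemoglobin | last value | last value (same) |
| RBC-dependent, hemoglobin | last value, even if drawn after a transfusion | value before the latest transfusion, or the lowest |
| Platelet-independent | one count | mean of two counts |
| Platelet-dependent | one count, even if soon after a transfusion | mean of two counts outside the post-transfusion period, or the lowest |
| Neutrophils | last value | not defined |

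Later values are restricted to absence of transfusion. SAP 2.5.1 gives the windows for regular assessments: "Platelet transfusion: 7 days preceding the assessment of platelet count", and 14 days for RBC. Only SAP 2.1.3 has a stated scope that reaches the count-change endpoint.

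**3. Effect in one subject.** Let B be the untransfused baseline, r the transfusion rise remaining in the last pre-dose value, and Y the later value.

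- Change under 2.5.1: Y − B
- Change under 2.1.3: Y − (B + r)
- Difference: −r

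Illustration for hemoglobin, all values assumed: B = 60 and Y = 80 g/L. Under 2.5.1 the change is +20. Under 2.1.3 it is 80 − 70 = +10 for r = 10, +5 for r = 15, and 0 for r = 20.

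Illustration for platelets (×10^9/L, assumed): B = 8 and Y = 30. Under 2.5.1 the change is +22. Under 2.1.3 it is +17, +12, +2 or −8 for r = 5, 10, 20 or 30.

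**4. Effect on the mean.** If a share p of the subjects summarized at a visit is affected, the mean shifts by −p × r.

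| p | r = 5 g/L | r = 10 g/L | r = 20 g/L |
|---|---|---|---|
| 25% | −1.25 | −2.5 | −5 |
| 50% | −2.5 | −5 | −10 |
| 75% | −3.75 | −7.5 | −15 |

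Both p and r are assumptions. At later visits p counts only subjects with a value outside the transfusion window, so it need not equal the share transfused before Day 1.

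**5. A smaller difference in precision.** With independent measurements of equal variance s², one baseline count gives a change variance of 2s² and a mean of two gives 1.5s². The ratio is 1.33 (SD ratio 1.15). This is extra noise, not bias, and it also applies to platelet-independent subjects.

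**The case against.** **Specific over general.** The 2.5.1 definitions have their own headings and are not expressly limited to the primary endpoint. Moreover, Table 2-2 judges transfusion-dependent subjects on transfusions, so the count baselines defined for them do no work in their platelet or red-cell response. That suggests they were written for something else, and change in counts is a natural candidate. This is fair evidence of intent, but the SAP does not say so, and 2.1.3 names efficacy outright.

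**The restriction may cover the baseline too.** The words on absence of transfusion could apply to every value, the baseline included. That is possible, but it would leave some subjects without a baseline or create a third one.

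**The contrast is less clean than it looks.** Later hemoglobin need only be outside a 14-day window, and the 2.5.1 platelet fallback may itself be a post-transfusion count. Protocol 8.4.1 requires hematology before supportive therapy, which removes a same-visit effect but not one from earlier days. These points limit the size of the problem; they do not remove it.

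**Responder status.** A reader might infer that one subject could be a responder on one baseline and not on the other, or might compare the bias with the 15 g/L hemoglobin criterion. The documents do not support this. The 15 g/L and 20 × 10^9/L rises apply only to transfusion-independent subjects. Anyone transfused just before Day 1 is by definition dependent for that product and is judged on transfusions. Response also has its own baseline rules, and the primary analysis uses the investigator's assessment.

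**Purpose.** The summaries are descriptive, in a single-arm estimation study without a hypothesis test. This limits the consequence.

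**Conclusion.** The point holds for the secondary count-change summaries and plots. Two efficacy baselines stand in the SAP without precedence, and the literal reading of 2.1.3 can subtract a transfused value from values restricted to absence of transfusion. On that reading each affected subject's change is understated by the residual rise r and the mean by p × r. An assumed hemoglobin rise of 10-20 g/L in half the subjects gives 5-10 g/L.

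A reader might go further and state that the reported changes are biased downward. That is not established. It depends on the analysis having followed 2.1.3, on a sample having been drawn between the transfusion and the first dose, and on values of p and r that the documents do not give. The Week 26 primary result is outside the point.

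**What to change.** - **SAP 2.1.3:** keep the last-available rule as the default, including for neutrophils, and add that the 2.5.1 platelet and hemoglobin baselines override it for all efficacy analyses.
- **SAP 2.7.1 and 2.7.2:** name those baselines for the count-change endpoint.

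Restricting 2.1.3 to safety would be the wrong edit. Neutrophils have no baseline in 2.5.1, and the neutrophil criterion in the primary endpoint is a rise from baseline.

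The text cost is a few sentences, since the definitions are already written and the programmed response in SAP 2.5.4 already draws on laboratory and transfusion records. There are two real costs. First, the 2.5.1 hemoglobin baseline is a pre-transfusion or lowest value, so later values just outside the 14-day window may slightly overstate the change; a table footnote should say so. Second, this SAP version precedes the final database lock and follows versions for the primary and updated analyses. Change tables already produced must be checked for the baseline they used and reconciled if it differs.

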All adverse events must be treated appropriately. Treatment may include one or more of the following:

- Dose not changed
- Dose Reduced/increased
- Drug interrupted/withdrawn
- 6. its outcome
  - a. not recovered/not resolved;
  - b. recovered/resolved;
  - c. recovered/resolved with sequelae;
  - d. fatal; or unknown.

If the event worsens, the event should be reported a second time in the CRF noting the start date when the event worsens in toxicity. For grade 3 and 4 adverse events only, if

improvement to a lower grade is determined a new entry for this event should be reported in the CRF noting the start date when the event improved from having been Grade 3 or Grade 4.

Conditions that were already present at the time of informed consent should be recorded in medical history of the subject.

Adverse events (including lab abnormalities that constitute AEs) should be described using a diagnosis whenever possible, rather than individual underlying signs and symptoms.

Adverse event monitoring should be continued for at least 30 days following the last dose of study treatment.

Once an adverse event is detected, it must be followed until its resolution or until it is judged to be permanent (e.g. Continuing at the end of the study), and assessment must be made at each visit (or more frequently, if necessary) of any changes in severity, the suspected relationship to the interventions required to treat it, and the outcome.

Information about adverse drug reactions for the investigational drug can be found in the Investigator's Brochure (IB).

Abnormal laboratory values or test results constitute adverse events only if they fulfill at least one of the following criteria:

- they induce clinical signs or symptoms
- they are considered clinically significant
- they require therapy

Clinically significant abnormal laboratory values or test results must be identified through a review of values outside of normal ranges/clinically notable ranges, significant changes from baseline or the previous visit, or values which are considered to be non-typical in subjects with the underlying disease.

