### **Adverse events**

All information obtained on adverse events will be displayed by subject.

The number (and percentage) of subjects with treatment emergent adverse events (events started after the first dose of study medication or events present prior to start of the first dose of study medication but increased in severity based on preferred term) will be summarized in the following ways:

- by treatment, primary system organ class and preferred term.
- by treatment, primary system organ class, preferred term and maximum severity.

Separate summaries will be provided for study medication related adverse events, death, serious adverse events, other significant adverse events leading to discontinuation and adverse events leading to dose adjustment.

The number (and proportion) of subjects with adverse events of special interest will be summarized.

A subject with multiple adverse events within a primary system organ class is only counted once towards the total of the primary system organ class.

Summary tables for adverse events (AEs) will include only AEs that started or worsened during the on-treatment period, the treatment-emergent AEs.

The incidence of treatment-emergent adverse events (new or worsening from baseline) will be summarized by system organ class and or preferred term, severity (based on Common Terminology Criteria for Adverse Events (CTCAE) version 4.03 grades), type of adverse event, relation to study treatment.

Serious adverse events, non-serious adverse events and adverse events of special interest (AESI) during the on-treatment period will be tabulated.

All deaths (on-treatment and post-treatment) will be summarized.

All AEs, deaths and serious adverse events (including those from the pre and post-treatment periods) will be listed and those collected during the pre-treatment and post-treatment period will be flagged.

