2.8.1 Adverse events (AEs)

Coding and grading

Adverse events will be coded using the Medical dictionary for regulatory activities (MedDRA) Terminology and their severity assessed according to the Common Terminology Criteria for Adverse Events (CTCAE) version 4.03.

General rules for AE Reporting

AE summaries will include all AEs occurring during on treatment period. All AEs collected in the AE (e)CRF page will be listed along with the information collected on those AEs e.g. AE

relationship to study drug, AE outcome etc. AEs with start date outside of on-treatment period will be flagged in the listings.

AEs will be summarized by number and percentage of subjects having at least one AE, having at least one AE in each primary system organ class (SOC) and for each preferred term (PT) using MedDRA coding. A subject with multiple occurrences of an AE will be counted only once in the respective AE category. A subject with multiple CTCAE grades for the same preferred term will be summarized under the maximum CTCAE grade recorded for the event. AE with missing CTCAE grade will be included in the 'All grades' column of the summary tables.

In AE summaries, the primary system organ class will be presented alphabetically and the preferred terms will be sorted within primary SOC in descending frequency. The sort order for the preferred term will be based on their frequency.

The following adverse event summaries will be produced for AEs occurring during the on-treatment period; overview of adverse events and deaths, AEs by SOC and PT, summarized by maximum CTCAE grade, summarized by relationship (all AEs and AEs related to study treatment), seriousness (SAEs and non-SAEs), leading to treatment discontinuation, leading to dose interruption/changes, requiring additional therapy and leading to fatal outcome.

Furthermore, AE occurring during the on-treatment period will be summarized by subgroup defined by age group (<65 years and \geq 65 years), gender (male and female) and concomitant use of CsA and anabolic steroids at baseline (Yes and No) (see [Section 2.2.1](#)). These summaries include: AEs by SOC and PT, AEs with suspected relationship to study drug by SOC and PT and SAEs by SOC and PT. These subgroup analysis will not be reproduced for final CSR.

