5.1.2 AE, ConMeds and safety assessment date imputation

Table 5-1 Imputation of start dates (AE, CM) and assessments (LB, EG, VS)

Missing Element	Rule
day, month, and year	
• No imputation will be done for completely missing dates
day, month	
• If available year = year of study treatment start date then
◦ If stop date contains a full date and stop date is earlier than study treatment start date then set start date = 01JanYYYY
◦ Else set start date = study treatment start date.• If available year > year of study treatment start date then 01JanYYYY• If available year < year of study treatment start date then 01JulYYYY
day	
• If available month and year = month and year of study treatment start date then
◦ If stop date contains a full date and stop date is earlier than study treatment start date then set start date= 01MONYYYY.
◦ Else set start date = study treatment start date.• If available month and year > month and year of study treatment start date then 01MONYYYY• If available month and year < month year of study treatment start date then 15MONYYYY

Table 5-2 Imputation of end dates (AE, CM)

Missing Element	Rule (*=last treatment date plus 30 days not > (death date, cut-off date, withdrawal of consent date))
day, month, and year	
• Completely missing end dates (incl. ongoing events) will be imputed by the end date of the on-treatment period*
day, month	
• If partial end date contains year only, set end date = earliest of 31DecYYYY or end date of the on-treatment period *
day	
• If partial end date contains month and year, set end date = earliest of last day of the month or end date of the on-treatment period*

Any AEs and ConMeds with partial/missing dates will be displayed as such in the data listings.

Any AEs and ConMeds which are continuing as per data cut-off will be shown as 'ongoing' rather than the end date provided.

The above imputations are only used for analyses of time to and duration of AEs and concomitant medications.

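### The SAP's start-date rule for treatment-emergent AEs could count a grade 3/4 event that began before first dose and improved on treatment

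*SAP*

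**What the plan says.** **Collection.** Protocol 10.1.1 collects AEs from informed consent onward, and screening runs from Day -30 to Day -1 (protocol Table 8-1). Conditions already present at consent go to medical history. An AE that worsens is reported a second time with the date of worsening. For grade 3 and 4 AEs that improve, "a new entry for this event should be reported in the CRF noting the start date when the event improved".

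**SAP definition.** SAP 2.1.3 sets the on-treatment period as "from date of first administration of study treatment to 30 days after date of last actual administration of study treatment". It then states that "summary tables for adverse events (AEs) will summarize only on-treatment events, with a start date during the on-treatment period", and calls these treatment-emergent. SAP 2.8.1 uses the same test and adds that "AEs with start date outside of on-treatment period will be flagged in the listings".

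**Protocol definition.** Protocol 12.5.2 has two formulations. Its opening text gives the same start-date sentence as the SAP. Its Adverse events subsection is stricter: it admits "events present prior to start of the first dose of study medication but increased in severity based on preferred term", and later says "Summary tables for adverse events (AEs) will include only AEs that started or worsened during the on-treatment period, the treatment-emergent AEs".

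**Partial dates.** SAP Table 5-1 imputes partial AE start dates by comparing them with the treatment start date. The section closes with "The above imputations are only used for analyses of time to and duration of AEs and concomitant medications".

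**The concern.** A start-date test works for worsening, because the new entry carries the date of worsening. It fails for improvement, because the entry recording a lower grade also carries a new date and the test cannot tell the two apart. No SAP sentence links an improvement entry to the event it continues, or removes it from the treatment-emergent set. A grade 3 or 4 AE that arose in screening and eased after first dose could therefore appear as a new on-treatment AE.

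Safety is in the study title and is a secondary objective, and the results are meant to support registration. In a single-arm study of about 20 subjects, the AE tables are read row by row, so one misclassified subject is visible.

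The closing sentence of SAP 5.1.2 leaves a smaller gap in the same flag. Where a partial start date could fall on either side of a boundary of the on-treatment period, no stated rule decides the AE's status.

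**Working it through.** The plan states no figure for this point. The check applies each written rule to hypothetical subjects, using the SAP's study-day convention.

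**Inputs**
- On-treatment window: first dose (Day 1) to last dose plus 30 days (SAP 2.1.3).
- New dated entry on worsening, and on improvement from grade 3 or 4 (protocol 10.1.1).
- Start-date rule (SAP 2.1.3; opening of protocol 12.5.2).
- Started-or-worsened rule by preferred term (Adverse events subsection of protocol 12.5.2).
- One count per subject, at the maximum grade for the preferred term (SAP 2.8.1).
- Planned N of about 20 (SAP Section 3).

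**Step 1. Apply both rules**

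| Subject | CRF entries, same preferred term | Start-date rule | Started-or-worsened rule |
|---|---|---|---|
| A | Grade 3 on Day -10; grade 2 on Day 20 | 1 | 0 |
| B | Grade 2 on Day -10; grade 3 on Day 20 | 1 | 1 |
| C | Grade 3 on Day 10; grade 2 on Day 20 | 1, at grade 3 | 1, at grade 3 |

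Subject A is the problem case. The Day 20 entry starts inside the window, so the start-date rule counts it. Grade 2 does not exceed grade 3, so the stricter rule does not. Subject B shows that worsening is handled alike. Subject C shows that an event starting after first dose is not double-counted, because two on-treatment entries collapse to one count at the higher grade.

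**Step 2. See whether another SAP rule removes A's entry**
- The once-per-subject, maximum-grade rule prevents double counting but leaves A's single on-treatment entry in place. If the maximum grade were taken over the pre-dose entry too, A would be shown at grade 3. The SAP does not say.
- The first-episode onset rule in SAP 2.8.1 is written for the table of AEs by time period. It does not decide which AEs are on treatment.

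**Step 3. Size**

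Increase in a preferred-term row = 100 × k / 20, where k is the number of subjects like A with no other on-treatment entry for that term.
- k = 0: 0 points
- k = 1: 100 × 1 / 20 = 5 points
- k = 2: 100 × 2 / 20 = 10 points
- k = 3: 100 × 3 / 20 = 15 points

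The documents give no value for k, so these lines show scale and are not a forecast.

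**Step 4. Partial start dates**

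If month and year are known, they settle the status unless the month contains first dose or the end of the window. If only the year is known, the same holds for the year. The gap is confined to those boundary cases. Table 5-1 would resolve them if SAP 5.1.2 allowed its use for the flag. Wholly missing start dates are not imputed by Table 5-1 in any case.

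**The case against.** **Events, not records.** SAP 2.1.3 speaks of events with an on-treatment start, and protocol 10.1.1 describes the improvement entry as belonging to the same event. A programmer could fairly treat the onset as pre-dose and exclude subject A. This stands to the extent that the miscount is a possible result of the text and not a certain one. The SAP gives no instruction either way.

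**An undeclared departure from the protocol.** A reader might infer this from SAP Section 4, which declares no change. The documents do not support it. The opening of protocol 12.5.2 has the same start-date sentence, so the conflict lies inside the protocol and the SAP took one of its two wordings.

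**Narrow exposure.** This stands. Cytopenias present at consent belong in medical history and have no AE entry to improve from. Only AEs arising in the weeks between consent and Day 1, reaching grade 3 or 4, still present at first dose and improving later are exposed. Laboratory abnormalities count as AEs only if symptomatic, clinically significant or needing therapy. Subjects with clinically significant infection are excluded.

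**Limited consequence.** This also stands. The analysis is descriptive and the error overstates harm. All AEs are listed, with pre-treatment ones flagged, so the original entry can be found. A reader might also expect the table of drug-related AEs to be inflated. That needs a suspected relationship for an event that began before any dose, which is unlikely.

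**Partial dates.** It would be too strong to say that any AE with a missing start day loses its flag or drops out. Outside the boundary months the status is known without imputation.

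**Conclusion.** The point holds as a gap in the definition. As written, the SAP's start-date rule can count a pre-dose grade 3 or 4 AE that improves on treatment, while the stricter of the protocol's two formulations would not. The two have to be reconciled, and the SAP is the place to do it.

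The size is 5 percentage points on one preferred-term row per affected subject, assuming 20 treated subjects and no other on-treatment entry for that term. How many subjects are affected cannot be learned from the documents. It is probably few and may be none, so a claim that rows will rise by any particular amount has no support. The direction is known: harm is overstated. The partial-date gap is secondary and confined to dates that straddle first dose or last dose plus 30 days. Neither matter touches the primary efficacy result.

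**What to change.** 1. In SAP 2.1.3 and 2.8.1, define a treatment-emergent AE as one that starts in the on-treatment period and is either new or, where the same preferred term was present at first dose, of a higher grade than before first dose. This restores the condition in the Adverse events subsection of protocol 12.5.2.
2. In the same place, state that an entry made only to record improvement of a pre-dose event is not treatment-emergent. A comparison by subject, preferred term and grade is enough; no CRF field linking entries is assumed.
3. Say whether the maximum-grade rule uses on-treatment entries only.
4. Amend the last sentence of SAP 5.1.2 so that the Table 5-1 start-date imputation also sets the on-treatment flag.
5. Record in SAP Section 4 which of the protocol's two formulations is followed.

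**Cost.** A few SAP sentences and one derivation step on dates and grades already collected. This SAP version precedes the final database lock, and SAP 2.8 has all safety outputs except subgroups generated again for the final CSR. The document history lists no change to the treatment-emergent definition, so the primary and updated CSR tables were presumably built on the start-date rule. The final AE tables may therefore differ slightly from them, and any difference should be footnoted.
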